- Upload the ZIP folder to the Uveitis Reading Center server:

5.4.5. Required patient assessments—Zeiss Cirrus

For our study, one of each of the following scans is required for each eye:

- **Macular Cube Scan**
- **5 Line Raster scan centered on the macula**

5.4.7. Obtaining retinal thickness data—Zeiss Cirrus

- Obtain Macular Thickness analysis
- Obtain 5 Line Raster analysis
- Record central subfield thickness on data sheet

Be sure to complete analysis of data and record information on data collection form as soon as possible. This will ensure that the treating physician will be able to use the SD-OCT results in real time to determine if macular edema is present or not.

5.4.8. Saving/Exporting data—Zeiss Cirrus

- All scans should be saved and archived at each study site on the Zeiss Cirrus SD-OCT unit. This raw data should also be saved onto a separate removable hard drive so that it is available for export and review at a later date.
- The following images should be uploaded to the server of the Uveitis Reading Center for review.
 - Under *Records* select *Export Exams*
 - Browse to folder where to save files
 - Search for the subject to export
 - Under *Exam Export* select the *Eye(s)* and *Exam Type* for the visit you want to export
 - Select *Export*
 - Label the file with patient’s unique study ID, visit number, and date of visit, example: “FAST_1Q001_BL_10AUG2012_IB”
 - Fill out transmittal form
 - Compress the folder containing the image files for both eyes and the Transmittal form in ZIP format
- Upload the ZIP folder to the Uveitis Reading Center server:

5.4.9. OCT operator qualifications

Prior to the study start date, at least 2 personnel who will be responsible for obtaining SD-OCT scans at each site should be identified. These individuals should have prior experience with operation of either the Heidelberg SD-OCT or Zeiss Cirrus SD-OCT instrument for routine clinic purposes. Personnel from the coordinating center will go to each

site before that start of the trial to meet with these technicians to review all required OCT procedures specified in our protocol. OCT operators must be able to demonstrate ability to obtain quality scans as well as knowledge of the study protocol.

5.5. Fundus Photography

Color fundus photography will be performed at baseline, 6 months, 12 months or treatment failure. Photos will include fundus reflex images and non-stereoscopic fundus images. Images should be uploaded to: <http://eyehealthusf.org/upload/index.php> according to instructions in UPRC manual.

Vitreous haze will be graded according to the NEI and Miami scales by masked graders. Photographers will need to be certified by the Uveitis Photograph Reading Center prior to obtaining photos for our study. Please see UPRC manual (Appendix E) for instructions on certification and obtaining study photos.

5.6. Laboratory measurements

Hematology and serum chemistry will be monitored in all patients prior to enrollment and throughout participation in the study. Each of the participating sites has an accredited onsite laboratory where all blood draws and laboratory measurements will be performed. The following will be measured and recorded on the Laboratory Report Form (Section A.8) for each:

Hematology

- Hemoglobin and/or hematocrit
- Platelet count
- White blood cell count (WBC)
 - % neutrophils; % lymphocytes
 - CD4 lymphocyte count ([REDACTED] sites only, at Baseline, Month 3, 6, & 12)

Serum Chemistry

- SGOT (AST)
- SGPT (ALT)
- Creatinine
- Serum or urine pregnancy test

Laboratory measurements used for baseline visits should be collected 4 weeks prior to enrollment. Those used for follow-up visits may be collected at any time within the study visit window. Laboratory measurements must be collected at each study visit.

All abnormal values will be reported on the Adverse Event Checklist (Section A.10) and monitored for resolution on the Adverse Event Log. Abnormalities which result in a non-serious adverse event (i.e. AST or ALT increasing to twice the upper limit of normal) will result in immediate stopping of study medications. As these abnormalities are often reversible, patients will be allowed one month to regain eligibility. If the lab results have returned to normal within one month, patients may be re-administered the study drug according to protocol. Labs can be checked prior to one month, and if normal, treatment can resume. Otherwise, treatment failure will be declared and patients may be treated according to best medical judgment of physician. They should still be followed for their 6th months visit and be treated according to the best medical judgment of their physician.

Laboratory abnormalities which meet the designated threshold of a severe adverse event (SAE) will result in immediate stopping of study medications, and should be reported on the Serious Adverse Event Narrative form (Section A.12). Treatment failure will be declared, and patients will be treated according to the best medical judgment of their physician, but still follow-up for 6 months. If a lab SAE occurs, patients will not switch to Phase II.

6. Adverse events

6.1. Non-serious adverse event (AE) *see the adverse event checklist (Section A.10)

Non-serious adverse events may include any unfavorable medical occurrences in patients who have ever received study medication, regardless of any causal relationship with treatment. Examples may include*:

- Increased intraocular pressure (>24 mm Hg)
- Abnormal lab findings (≥ 2 times but < 5 times the upper limit of normal AST or ALT, rise in creatinine to ≥ 1.5 to < 2 mg/dL, reduction of white blood cell count to below 2.5)
- Concurrent accident or illness
- Increase in the frequency and severity of symptoms of a pre-existing condition
- Side effects such as gastrointestinal upset, nausea, vomiting, fatigue

6.2. Serious adverse event (SAE) *see the adverse event checklist (Section A.10)

Serious adverse events include any medical occurrence that results in the following outcomes, or any other adverse event classified as severe*:

- ≥ 5 times the upper limit of normal AST or ALT
- Death
- Non-elective surgery or hospitalization for any reason
- Myocardial infarction or stroke
- Life-threatening adverse drug experience or any life threatening event
- Persistent or significant disability or incapacity
- Cancer
- Seizure
- Congenital anomaly/birth defect
- Disability or permanent damage
- Required intervention to prevent permanent impairment/damage

6.3. Adverse event reporting

Non-serious and serious adverse events will be recorded at each study visit on the appropriate form (Adverse Event Checklist and Log, Sections A.10-A.11). An adverse event log will be maintained for each patient to record the onset and resolution of any adverse events. The Adverse Event Checklist will initially be completed by the study coordinator while meeting with the patient at the beginning of each study visit. If there are any reported symptoms (not only severe symptoms), the study physician will review them with the patient while remaining masked to determine if any action is needed.

In case of a Serious Adverse Event (SAE), the Serious Adverse Event Narrative Form (Section A.12) will be completed by the Investigator and submitted to the Medical Monitor, [REDACTED] Principal Investigator [REDACTED] and the Coordinating Center Manager [REDACTED] within 24 hours of the SAE. Information recorded on this form will include the nature of the

event, date of onset, date of resolution, date of notification to Medical Monitor, and action taken. The Medical Monitor will review, sign, decide if the serious adverse event was related to the study drug, and collect additional information if needed.

If any serious adverse event other than a laboratory abnormality occurs, treatment failure cannot be declared until the Medical Monitor judges that the SAE is related to the study drug. This will require the investigator notifying the Medical Monitor about the event, and the Medical Monitor contacting the investigator regarding his determination. The Medical Monitor will determine two things: 1) whether this is a true treatment failure because the SAE is likely related to the study drug, and 2) whether it is safe to switch the patient to Phase II. If it is not safe to switch the patient will be treated with best medical judgment and still be followed for 6 months.

If the investigator thinks the SAE is related to the study drug, he/she can stop the study medication anytime (including prior to determination of treatment failure by the medical monitor). If the investigator thinks treatment failure is likely (prior to hearing from the Medical Monitor) they should obtain all study assessments, which would be collected at a treatment failure visit. However, the investigator will wait to complete the Treatment Assessment Form and officially declare treatment failure, until they are instructed to do so by the Medical Monitor.

Any significant study drug-related adverse events will be reported by the coordinating center to the FDA and CHR office as appropriate. The principal statistician will inform the DSMC of serious adverse events by arm every six months.

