2.4. Randomization and masking

Block randomization of the patients will ensure that an equal number of patients are randomized to each study arm at each site. Randomization lists will be created by the biostatistician ([REDACTED]) and accessed online via REDCap database. The following people will be able to access to the list of patients who have been randomized through the REDCap database:

Emergency Contact Personnel*

[REDACTED]

*Emergency contacts will log into REDCap to consult the list of randomized patients in case of an emergency in which unmasking is necessary for patient safety and [REDACTED] of the DCC cannot be reached.

Data Coordinating Center (DCC) Personnel

[REDACTED]

The study coordinators (listed below) will be aware of patient treatment assignment and will have a copy of the patient ID list for their site; however, they will not know future treatment assignments prior to randomizing patients. After consenting patients for enrollment and confirming all eligibility requirements have been met, study coordinators will log into REDCap and perform the randomization. Study coordinators will then give patients their assigned treatment.

The following study coordinators will have access to REDCap to perform randomizations but will not know the treatment assignments prior to randomizing patients:

[REDACTED]

[REDACTED]

[REDACTED] will act as study coordinator to [REDACTED] patients, as well as Coordinating Center Manager overseeing all other sites. [REDACTED] will have access to the randomization lists for other sites, in order to check patient treatment assignment as a quality assessment and manage distribution of medications to all sites.

All patients and study coordinators will be unmasked to treatment assignment after enrollment, as the two study drugs are different in appearance and must be administered on different weekly schedules. Study ophthalmologists performing the clinical eye exams, as well as visual acuity examiners, OCT operators, fundus photographers and fundus graders will be masked to treatment assignment to prevent bias in study outcomes. The [REDACTED] [REDACTED] investigational drugs department will purchase and supply mycophenolate mofetil and methotrexate.

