*If the patient is experiencing intolerable side effects, the study coordinator and patient will speak to the doctor about the possibility of a dose reduction, without revealing the name of the medication or the dosing instructions. The study doctor will then decide if the dose reduction should be done and inform the study coordinator and patient. The study coordinator will then provide the patient with new dosing instructions, away from sight of study physician. A dose reduction is not mandatory but is encouraged in the setting of intolerability.

- The patient will then complete the study assessments, in the following order:
 - Visual Acuity Assessment
 - Slit lamp front of the eye exam and intra-ocular pressure
- The patient's eyes will then be dilated and the following assessments will be completed, in any order**:
 - Posterior segment exam
 - OCT imaging
 - Fundus photography
 - Fluorescein angiogram (not a study assessment, but if performed results should be recorded)
 - Laboratory measurements
- After completion of the study visit, the patient will meet with the coordinator, review scheduling for the next study visit, and retrieve their medication.

**It is essential that visual acuity measurements, front of the eye exams and intra-ocular pressure are completed *before* dilation of the eyes.

Data handling and data entry

After completion of each study visit, study coordinators at all sites will scan data collection forms and send them electronically in PDF format to the study email address ([REDACTED]). Hard copies of the forms should be kept in a secure location at each site. Study staff at [REDACTED] will perform double data entry of the PDF forms into a web-based REDCap database from which data can be electronically extracted for analysis. See section 7 for further details on the data entry process.

4. Study visits

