5.3.3. Inter-observer variation of ocular inflammation

At Baseline (Phase I and Phase II) the 6th month study visit (Phase I and Phase II), the 12th month study visit (Phase I), or at treatment failure (whichever is earlier), inter-observer agreement on slit lamp observations and fundoscopic exam will be assessed. Coordinators will arrange for two certified study physicians to measure anterior chamber cells, anterior chamber flare, vitreous cells, vitreous haze, and retinal/choroidal lesions at the Month 6 and 12 visit or at declaration of treatment failure. The inter-observer variation will be reported. The primary study ophthalmologist's measurements will be used for primary analysis.

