9.1. Ophthalmologist

- Note: whenever possible, the primary study ophthalmologist should be the same person across all a patient's study visits, for consistency of measurements
- Responsible for enrolling study subjects
- Provide information for completing the clinical examination forms
- Obtain written consent from the subjects with the help of study coordinator
- Initiate study medication as per the randomization
- Responsible for the care of the patient throughout the course of the study
- Manage adverse events

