4. *Quality of life.* For a power calculation, we consider the SF-36 questionnaire, which has two scales, the MCS and the PCS. The raw score standard deviation will be assumed to be 8.4 points; we assume a correlation between baseline and six months of 0.6.^{16, 17} Assuming that the baseline score will “explain” roughly 36% of the variance allows us to assume a corrected raw score standard deviation of 6.72 in a simplified calculation in which we treat the analysis as a T-test. The same power calculation formula used in (3) above reveals that **our sample size provides approximately 80% power to detect a raw score difference of roughly 2.57 between the two treatment groups.** This difference is roughly comparable to the small difference in scores found between intermediate uveitis patients and the general population¹⁶, a difference we believe to be more than sufficient to detect clinically significant results. Note that the population mean of this score is standardized to 50 on 0 to 100 scale. Similar analyses will be conducted for the vision related quality of life (i.e. NEI-VFQ-25 and the IND-VFQ).

5. *Rate of discontinuation.* Based on retrospective studies, we expect approximately 13% to discontinue methotrexate due to tolerability and 5% to discontinue due to safety (laboratory abnormalities or other serious adverse events). We expect approximately 4% to discontinue mycophenolate mofetil due to tolerability and 5% to discontinue due to safety.^{12, 18-20} For the purpose of the power calculation, we assume 10% loss to follow-up and consider only the comparison of discontinuation due to tolerability. **We use the power formula given in Freedman et al (p. 104) to calculate a power of 61% for this comparison.**³

6. *Macular edema.* Previous studies suggest approximately 38% of individuals with uveitis will manifest macular edema.²¹ **We have approximately 80% power to detect a difference of a factor of two in the final proportion of macular edema (19% vs 38%).**

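### The masked examiner reviews every reported symptom with an unmasked patient, and nothing says the inflammation grades must be recorded first

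*Combined protocol and SAP*

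**What the plan says.** Protocol 6.3 has the coordinator fill in the Adverse Event Checklist at the start of each visit. It then continues: "If there are any reported symptoms (not only severe symptoms), the study physician will review them with the patient while remaining masked". No procedure is given for how masking survives that conversation.

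The reviewing physician is also the grader. Protocol 2.4 lists among the masked staff "Study ophthalmologists performing the clinical eye exams, as well as visual acuity examiners". Protocol 9.1 gives the ophthalmologist the examination forms, the patient's care, and the duty "Manage adverse events". Two certified physicians grade at month 6, but under 5.3.3 it is the primary ophthalmologist's grades that count: their "measurements will be used for primary analysis".

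Protocol 3.3 sets out the visit. Coordinator check-in, including the adverse-event review, comes first. After that, "The patient will then complete the study assessments, in the following order": visual acuity and slit lamp, then dilation and the posterior examination. A footnote to the check-in item covers the case of a patient who cannot tolerate the treatment: "the study coordinator and patient will speak to the doctor about the possibility of a dose reduction, without revealing the name of the medication". The wider review in 6.3 has no place in this list.

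**The concern.** Patients and coordinators are unmasked, so the examiner's masking is the main protection for an endpoint that rests on clinical judgement. Control means a grade of 0.5+ or less for anterior chamber cells and vitreous haze, and the next grade, 1+, is a failure of control. Protocol 5.3.4 certifies graders who agree within one level, so the endpoint turns on a step no larger than the accepted disagreement between graders.

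An examiner's expectation could also have a direction. The Background reports retrospective series suggesting better control and tolerability on mycophenolate. If symptoms or their weekly or daily pattern let the examiner guess the arm, borderline grades could drift in favour of the expected winner.

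The protocol takes more care with a secondary outcome. In 5.2.2, visual acuity examiners are denied the patient's earlier examination and treatment results so as to limit bias. The grader of the primary outcome has no comparable shield from side-effect history.

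**Working it through.** **1. Do the safeguards reach symptoms?**
- Protocol 2.4: doctors take no part in labelling or handing out bottles, bottles are kept in dark bags, the coordinator is seen first and holds the calendars and bottles, and a deviation form is required if someone is unmasked.
- Protocol 3.1 and 3.3: patients are told not to mention the drug's name or dosing, and new dosing instructions are given away from the physician.
- None of these mentions symptoms or their timing. Methotrexate is taken one day a week and mycophenolate twice daily (Table 4).

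**2. Is there an order?** Section 6.3 does not place the physician's review before or after the examination. The dose-reduction talk in 3.3 is printed ahead of the assessments, but as a footnote, which is not a sequence rule. No section requires grades to be recorded first.

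**3. Which patients can be affected?** SAP 3.4.2 states that "we expect approximately 13% to discontinue methotrexate due to tolerability", against about 4% for mycophenolate. With 1:1 allocation, 0.13/(0.13 + 0.04) = 76% of patients stopping for intolerance would be on methotrexate. But protocol 2.5.1 rules out success after a tolerability failure, and SAP 3.2.2 scores discontinuation for intolerance as 0. Eye grades cannot alter those outcomes. Any grading bias acts on patients who have symptoms and continue, and the documents give no symptom rates by arm for them.

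**4. The plan's own sample size.** With 40% versus 60% success, two-sided alpha 0.05 and 80% power, a standard two-proportion formula gives 97 per arm, and 97/0.9 = 107.8, or 108 per arm and 216 in total. SAP equation (5) gives 2N = 196.2, and 196.2/0.9 = 218.0, close to 216. I therefore use 97 evaluable patients per arm.

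**5. Illustration of size.** The documents give no inputs, so these are assumptions:
- q = share of patients whose arm is inferred: 0.20 to 0.40.
- f = share of those whose grade is leaned, up in one arm and down in the other: 0.10.
- p = success rate in both arms (no true difference): 0.50.

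An upward lean can change only a patient who would otherwise fail, and a downward lean only one who would otherwise succeed:
- Bias = q × f × (1 − p) + q × f × p = q × f
- q = 0.20: 0.20 × 0.10 = 0.02
- q = 0.40: 0.40 × 0.10 = 0.04

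Standard error = sqrt(2 × 0.25/97) = 0.0718.

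Two-sided rejection rate = Φ(−1.96 + bias/SE) + Φ(−1.96 − bias/SE):
- Bias 0.02: ratio 0.279, giving 0.046 + 0.013 = 0.059
- Bias 0.04: ratio 0.557, giving 0.080 + 0.006 = 0.086

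A separate calculation, shifting one arm's success rate from a common 40-60% with 97.2 per arm, agrees: a 2-point shift gives about 6% and a 5-point shift about 11%. Both calculations ignore the site random effect, the permutation test and the interim looks.

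**6. Are the second examiner's grades used?** The Secondary Clinical Eye Exam Form is scheduled at months 6 and 12 and at treatment failure (4.2). Section 5.3.3 uses it only to report inter-observer variation. None of the SAP's sensitivity analyses (3.2.2 item 11, 3.3.1, 3.5, 3.5.1) uses these grades.

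**The case against.** The other side has good points, and most of them stand.

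- **Masking is taken seriously.** The measures in step 1 are substantial. It would be wrong to say that masking rests only on asking patients not to name their drug. The gap is limited to symptoms and their timing.
- **Symptoms may not identify the drug.** A reader might infer that side effects are drug-specific. The documents do not say so: protocol 6.1 lists generic effects and assigns none to a drug, and all patients also start prednisone. That symptoms carry information about the arm is an inference from the dosing pattern and the expected tolerability difference.
- **The order is open.** A reader might take 3.3 and 6.3 to place the symptom talk before grading. They do not. A site may already grade first.
- **The 13% versus 4% is weak evidence.** It is a discontinuation rate, not a symptom rate, and those patients are failures regardless of grade.
- **A larger bias is tempting.** If every lean changed the result, the bias would be 2 × 0.10 × (0.20 to 0.40) = 4-8 points, with a false-positive rate of about 9-20%. That counts leans which cannot change anything, such as an upward lean in a patient who already succeeds.
- **Grading first is a partial remedy.** Under 9.1 the same ophthalmologist should, where possible, see the patient throughout, and will remember symptoms from earlier visits.

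What these points do not remove is the absence of any rule on order, and a second set of grades that goes unused.

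**Conclusion.** The concern holds as a preventable risk. The plan puts symptom review and primary-outcome grading in the same masked role, does not say which comes first, and makes no analytic use of the independent grades it collects. It does not show that examiners will be unmasked.

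The illustration (a bias of at most about 2-4 points, a false-positive rate of about 6-9%) rests wholly on the assumed q and f. Within those inputs it is an upper figure: success also requires control in both eyes, the corticosteroid limits and no earlier failure, so one borderline grade will often decide nothing. The case for acting rests on the low cost of the remedy, not on the size of a demonstrated bias.

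**What to change.** **1. Protocol 3.3 and 6.3.** Require the Clinical Eye Exam Form grades (anterior chamber cells, vitreous haze, retinal/choroidal activity) to be completed and signed before the physician's symptom review or any side-effect discussion at that visit. Clinical decisions stay as they are; only the order of recording changes.

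**2. SAP.** Add a sensitivity analysis of the primary outcome that replaces the primary ophthalmologist's month-6 grades with those of the second certified examiner under 5.3.3. State in the protocol that this examiner is not given adverse-event information. At present that examiner simply has no assigned part in the symptom review, which is not a safeguard.

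**Cost.** Steps are reordered within an existing visit, and one analysis is added on data already collected. The symptom discussion comes later in the visit. The gain from (1) is partial because of recall from earlier visits, which is why (2) is needed. Neither change undoes a futility failure that the same physician has already declared under 2.5.2.
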